In this project, an interventional case-control study will be undertaken in four middle sized counties in the south of Sweden. Based on the case control sample also a methodological study will be realized in order to test the measurements' validity and reliability, but also a descriptive qualitative content analysis study will be accomplished. All these measurements – called triangulation – are done in order to strengthen the case-control study as a power calculation is not relevant to do due to the restricted eligible/consecutive sample as well as the restricted time schedule. Finally, based on all available data, a cost-effectiveness analysis will be undertaken with the use of a decision analytic model.

Intervention

Standard treatment

In order to replace extracted teeth after radiotherapy, the standard treatment is temporary removable dental prostheses/dentures (partial or complete). Depending on the teeth remaining, those may be completely tooth or tissue supported, or tissue and tooth supported. Temporary partial dentures are completely out of acrylic. Efforts are made to design a self-cleansing partial denture that preserves the remaining teeth and oral structures. The chewing forces are distributed evenly over the entire remaining teeth and soft tissues. Oral health related quality of life in healthy patients wearing removable dentures has previously been shown (12).

Fixed dentures

The special treatment is to within a year after completed radiotherapy replace removable dentures with tooth- or implant-supported dentures. The special treatment will begin six months after completed radiotherapy, or later depending on the severity of the side effects. Tooth- and implant-supported dentures are accepted modalities in patients with total or partial edentulous (13, 14). Patients with head and neck cancers usually follow the dental implant protocol valid for healthy individuals (15, 16). However, the fixture installation will be within a year after finished radiotherapy, when the jaws are still well supplied.

Participants

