The study will take place in four middle sized counties in the south of Sweden. The intervention will include 30 patients with head and neck cancer recruited from a Department of Maxillofacial and Oral Surgery (the City of Jönköping, Jönköping County Council), and from the Department of Orofacial Medicine (the City of Stockholm, Stockholm County Council). Another 30 patients with the same disease will be matched controls recruited from another Department of Maxillofacial and Oral Surgery (the City of Linköping, County Council of Östergötland) and from five Departments of Orofacial Medicine (the Cities of Kalmar, Oskarshamn, and Västervik, Kalmar County Council; the Cities of Ljungby, and Växjö, Kronoberg County Council). If possible but not necessary, those controls may be prosthodontically rehabilitated with temporary removable dentures. The retest described in data collection study one will include ten patients diagnosed with head and neck tumor. All patients in the retest will be residents in the County of Jönköping.

The inclusion criteria are patients with head and neck tumours considered to receive radiotherapy, with or without combination of chemotherapy or surgery, good oncological prognosis at baseline ($\leq T2$). After referral from an ENT-specialist, those patients being diagnosed with dental infections and therapy planned for dental extraction(s) will be included.

The following general exclusion criteria will be applied: any communication problems; any comorbidity with poor prognosis; poor oncological prognosis (TNM-classification $>T2$) at baseline; imminent risk of recurrence; any technical, biological, or any other reasonable obstacle of treating patients with fixed dentures; and finally patients in the matched control group financing fixed oral prosthesis themselves.

Background data like sex, age, diagnosis, TNM-classification, hyposalivation, vertical jaw mobility, dysphagia, number and sites of extracted teeth, and weight will be investigated.

Study one – quantitative approach

Instruments

SF-36v2

SF-36v2 is a well established psychometric instrument with 36 items measuring eight domains of health-related quality of life: Physical function, physical role function, bodily pain, general health, vitality, social function, emotional role function, mental health. The two comprehensive indices – physical health and mental health - can be estimated for. The instrument is translated and validated into Swedish (17-19).

EQ-5D

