EQ-5D is an instrument containing five items measuring mobility, self-care, pain, role function, and anxiety/depression. There is also one item considering change of health condition and a VAS scale for general health. This instrument is also translated and validated into Swedish (20-22).

Oral health impact profile (OHIP)

OHIP-14 is an instrument consisting of 14 items (23). It was designed to provide a comprehensive measure of the dysfunction, discomfort and disability attributed to oral conditions. Validated Swedish versions of the OHIP-14 are available (24, 25).

General oral health assessment index (GOHAI)

GOHAI is a 12-item instrument originally developed for use with older adult populations, although more recently it has been used with populations of younger adults. It measures oral functional problems and also assesses the psychosocial impacts associated with oral disease (26). A Swedish version has been validated (27).

The Jaw Functional Limitation Scale (JFLS-8)

The JFLS-8 was developed for assessing limitations in mastication, jaw mobility, and verbal and emotional expression. It is recommended for clinical and research use in patient groups with varying functional limitations of the jaw. The instrument has been tested for reliability and validity (28, 29).

The Orofacial Aesthetic Scale (OAS)

The OAS consists of seven separate aesthetic aspects of the face, teeth, lips, and mouth — devoid of psychosocial aspects. These seven items create the OAS summary score. There is also an eight item, global assessment of overall impact. A Swedish version has

been validated (28, 30, 31).

Data collection

The written consent among with the instruments will be distributed to the patients at the clinic at baseline (before any treatment), appendix 4. The completed documents will be returned to a research coordinator/dental assistant at the Department of

Maxillofacial and Oral Surgery (the City of Jönköping, Jönköping County Council).

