Measurements and administration of the instruments after baseline follow the study protocol, appendix 13. The study protocol after completed radiotherapy states measurements at approximately 6 and 12 months respectively, or in severe cases after the prostheses have been used for one month. Those patients who receive the instruments by mail, will be requested to immediately respond to the instruments and return them to the research coordinator in attached envelopes (prepaid postage). A reminder is sent to the patient after one and two weeks if not responding. If necessary after another week, the patient will be contacted by telephone by the research coordinator. The patients weight will be recorded at the clinic, or self-reported by mail.

Data analysis

Parametric as well as non-parametric methods will be used in the statistical inference testing. Thus, for comparison between two groups the Student t-test and the Mann-Whitney U-test and between three groups or more Two-Way Analysis of Variance the Kruskal-Wallis One-Way Anova will be applied. For comparison of proportions between groups the Chi-square-test including standardized residual are to be used. For analysing changes over time the paired t-test or the Wilcoxon Signed Rank Test (for continuous variables) or the McNemar Test (for dichotomised variables) will be applied. For estimating relation between two continuous variables the Pearson test or Spearman

Rank Order Correlation will be used. For prediction, multiple and logistic regression are to be used and in order to adjust for confounding variables such as age logistic regressions also are to be used. The pre-chosen level of significance will be $p<0.05$ in all analyses.

Study two – qualitative approach

Interviews

A dental assistant experienced in methodological or subject experiences will interview the patients during approximately one hour twice. The dialogue will start with questions on general wellbeing, and then approaching oral health related quality of life. All the interviews will start with the question “How do you feel with regard to your health?”, followed by “Can you tell me more?”. Eventually the dental assistant asks, “How do you feel with regard to your mouth?” The interview will result in a detailed and exhaustive story from different point of views. All interviews will be recorded on minidiscs.

Data collection

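### Non-randomised groups are compared on scores with unadjusted tests, confounder adjustment is given to logistic regression, and no between-group test is stated to use the baseline score

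*Protocol*

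**What the plan says.** The Design and setting section describes the project this way: "an interventional case-control study will be undertaken in four middle sized counties in the south of Sweden". No randomisation is described. Under Participants, "The intervention will include 30 patients with head and neck cancer recruited from a Department of Maxillofacial and Oral Surgery" in Jönköping and from a clinic in Stockholm. "Another 30 patients with the same disease will be matched controls recruited from another Department of Maxillofacial and Oral Surgery" in Linköping and from clinics in Kalmar and Kronoberg counties. The matching variables are not named. One exclusion, for patients who pay for a fixed prosthesis themselves, applies to controls only.

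The Data analysis section of Study one gives each purpose its own methods:

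- Two groups: "for comparison between two groups the Student t-test and the Mann-Whitney U-test".
- Change: "For analysing changes over time the paired t-test or the Wilcoxon Signed Rank Test (for continuous variables"), with McNemar for dichotomised variables.
- Regression: "For prediction, multiple and logistic regression are to be used and in order to adjust for confounding variables such as age logistic regressions" are also to be used.
- Proportions: the chi-square test.

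Under Data collection, "the instruments will be distributed to the patients at the clinic at baseline (before any treatment"), and again at about 6 and 12 months after radiotherapy. The Participants section also lists "Background data like sex, age, diagnosis, TNM-classification, hyposalivation, vertical jaw mobility, dysphagia, number and sites of extracted teeth, and weight" as information to be gathered.

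**The concern.** When group is set by clinic and county, the groups may differ before any denture is fitted. The control-only exclusion is a further route to imbalance. The analysis therefore has to carry much of the control of confounding.

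The listed methods do not do this for the scores (OHIP-14, GOHAI, JFLS-8, OAS, SF-36v2). The two-group tests named take no covariates. The paired tests look within a group. The method given the task of adjustment, logistic regression, cannot take a score unless it is cut, and no cut-point is given. Multiple regression would suit scores but is listed for prediction. The most useful covariate, the same score before treatment, has no stated place in any between-group comparison.

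A baseline difference between counties could then pass into the 6- and 12-month comparison and be read as an effect of fixed dentures. With 30 per group, precision may be lost as well.

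**Working it through.** **Reading the text.** The protocol declines a power calculation, so there is no planned figure to reproduce. Setting purposes against methods:

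| Purpose | Method named | Suits a score? | Uses baseline or covariates? |
|---|---|---|---|
| Two-group comparison | t-test, Mann-Whitney | Yes | Not stated |
| Change over time | Paired t, Wilcoxon | Yes | Baseline, within a group |
| Prediction | Multiple and logistic regression | Multiple: yes | Covariates, for prediction |
| Confounder adjustment | Logistic regression | No, unless cut | Covariates; only age is named |

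No row gives a covariate-adjusted between-group comparison of a score.

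**Inputs for the size.** From the protocol: 30 per group and a 0.05 level. Assumed, because the protocol gives none: two-sided testing, normal scores with SD 1, no true effect, baseline-to-follow-up correlation r = 0.3 to 0.6, and baseline gap b = 0.3 to 0.5 SD. Here, unadjusted means a t-test on follow-up scores alone.

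**Scenario A: the gap shrinks to r × b at follow-up.**
- Unadjusted bias = r × b, from 0.3 × 0.3 = 0.09 SD to 0.6 × 0.5 = 0.30 SD.
- Baseline-adjusted bias = 0.
- Normal approximation to the rejection rate: Φ(m − 1.96) + Φ(−m − 1.96), with m = r × b / √(2/30). At r = 0.5 and b = 0.5, m = 0.25/0.258 = 0.97, giving 16.2%. Simulation gives 15.9%.

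**Scenario B: the gap persists in full.**
- Unadjusted bias = b, 0.30 to 0.50 SD.
- Baseline-adjusted bias = (1 − r) × b, from 0.4 × 0.3 = 0.12 SD to 0.7 × 0.5 = 0.35 SD.
- Change-score bias = 0.

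Simulated rejection rates with no true effect (40,000 trials per cell):

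| r | b (SD) | A: unadjusted | B: unadjusted | B: baseline-adjusted |
|---|---|---|---|---|
| 0.3 | 0.3 | 6.2% | about 21% | 13.1% |
| 0.3 | 0.5 | 8.7% | 47% to 48% | 27.0% |
| 0.5 | 0.3 | 9.0% | about 21% | 9.9% |
| 0.5 | 0.5 | 15.9% | 47% to 48% | 18.6% |
| 0.6 | 0.3 | 10.5% | about 21% | 8.8% |
| 0.6 | 0.5 | 21.0% | 47% to 48% | 15.1% |

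The baseline-adjusted model stays at 4.8% to 5.1% throughout A. The change-score t-test gives 7.9% to 20.3% in A and 4.8% to 5.1% in B.

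**Precision with no gap.** The unadjusted t-test detects 0.736 SD with 80% power (noncentral t). With baseline adjustment this becomes 0.736 × √(1 − r²):
- r = 0.3: 0.702 SD
- r = 0.4: 0.674 SD
- r = 0.5: 0.637 SD
- r = 0.6: 0.59 SD

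Four further covariates that explain nothing multiply this by about √(57/53) = 1.037. At r = 0.3, 0.702 then becomes 0.729 SD once the lost degrees of freedom are also counted.

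**If a score were cut to suit logistic regression.** For a true difference of 0.5 SD and a median split, the proportions are 0.599 and 0.401. By the normal approximation, power falls from 49% to about 33%. The protocol does not say scores will be cut, so this shows only what that route would cost.

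**The case against.** The strongest reply is that this reads a loose list too strictly. The confounder sentence says logistic regressions are also to be used, which need not make them the only means of adjustment, and multiple regression appears in the same sentence. McNemar and chi-square show that some binary outcomes are planned, and logistic regression is right for those. The section does not say whether the t-test is applied to follow-up values or to change, and a t-test on change would use baseline. A statistical analysis plan could settle this. Controls are called matched, which may limit any gap, and radiotherapy and extractions between baseline and follow-up could make r low. At r = 0.3 and b = 0.3 in scenario A the error is 6.2%, close to nominal.

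Part of this stands. A change-score t-test is not excluded, the error rates depend on assumed values, and silence on baseline alone would be a weak point. The precision gain is also small at low r: six covariates that explain nothing would give about 0.702 × √(57/51) = 0.742 SD, slightly worse than no adjustment.

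The main point is unaffected. The word also adds adjustment as a second use of logistic regression; it does not give multiple regression that task. Planned binary outcomes still leave the scores without an adjusted comparison. A later analysis plan using linear adjustment would have to go beyond what the protocol assigns.

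**Conclusion.** The concern holds and should be fixed. The protocol names a model that does not fit scores for confounder adjustment and states no between-group use of the baseline score, in a comparison where clinic and county determine treatment.

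The size is conditional on the assumed correlations and gaps. Across them, the unadjusted follow-up test exceeds 5% in both scenarios. Neither alternative is safe in both: baseline adjustment holds 5% if the gap shrinks with r, and the change score holds it if the gap persists. Both analyses are therefore worth having. Adjustment reduces bias but cannot be relied on to remove it, and no covariate set separates treatment from county or centre here. The protocol does not claim that within-group tests show a treatment effect, and that is not alleged.

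**What to change.** In the Data analysis section of Study one:

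1. State that each score at 6 and 12 months is compared between groups with a linear model containing group, the same score at baseline, age and a small pre-specified set of background variables already collected, for example diagnosis, TNM-classification and number of extracted teeth. Add the matching factors once the protocol names them. Keep the number of parameters low.
2. Report the adjusted mean difference with its 95% confidence interval.
3. Add a between-group analysis of change from baseline as a sensitivity check, and say that the two analyses are unbiased under different assumptions about the baseline gap.
4. Limit logistic regression to outcomes that are truly binary, and treat within-group paired tests as descriptive.
5. State that the comparison is non-randomised and that county or centre stays confounded with treatment whatever covariates are used.

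The cost is rewording, a little more analysis and a few degrees of freedom. Baseline scores and background variables are already collected; the matching factors must be stated before they can be used. No extra patients or visits are needed.

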is caused by poor vasculated bone. Teeth with poor prognosis should be extracted before radiotherapy begins, leading to impaired occlusion including dysfunctional aesthetics and mastication. The Swedish National Board of Health and Welfare regulations compensate extracted teeth with removable dental prostheses/dentures (8). However, using removable dentures in patients with hyposalivation after radiotherapy is complicated. Removable dentures retain poorly, or chafe the oral mucosa leading to pain in function. Also, there may be problems maintaining good dental and denture hygiene leading to dental caries and periodontitis.

To date, the impact of dental occlusion on these patients' quality of life is sparsely investigated. In one study, implant-retained mandibular overdentures in patients treated for oral cancers were followed over five years (9). Overall, the survivors' oral function and patient satisfaction were high and did not change. Impaired global health and quality of life were associated with concurrent comorbidity. Malnutrition, associated with increased morbidity and mortality, in patients treated for oral/oropharyngeal cancers was shown to impair physical functioning and hence quality of life (10). In this study dental status was poorly described, although dry mouth, pain in the mouth, and problems with social contact correlated well to malnutrition and fatigue. Speech after surgery was more impaired in patients with oral cancers than with oropharyngeal cancers because of loss of anatomically important articulatory structures leading to decreased quality of life. However, there are no prospective studies supporting better speech outcome after radiotherapy alone compared with surgery (11).

Therefore, the aim of this project was to evaluate the effect and cost effectiveness of prosthodontic rehabilitation on oral health related quality of life, general wellbeing, and nutrition in patients treated by radiotherapy, with or without combination of

chemotherapy or surgery against head and neck cancer.

Methods

Design and setting

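### A paired change from the pre-treatment baseline cannot by itself show a denture effect, and the group comparison that can is not tied to a score taken after radiotherapy and before the fixed denture

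*Protocol*

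**What the plan says.** All references are to the protocol.

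- **Baseline.** Under Study one, Data collection, the instruments are "distributed to the patients at the clinic at baseline (before any treatment), appendix 4".
- **Extractions.** The Introduction says: "Teeth with poor prognosis should be extracted before radiotherapy begins". Under Participants, "those patients being diagnosed with dental infections and therapy planned for dental extraction(s) will be included". Extraction is therefore still ahead when the baseline form is answered.
- **Follow-up forms.** Study one, Data collection, gives "measurements at approximately 6 and 12 months respectively, or in severe cases after the prostheses have been used for one month", and refers to appendix 13 for administration after baseline. Some forms go by post, with reminders after one and two weeks and a telephone call a week later if needed.
- **Start of fixed treatment.** Under Intervention, Fixed dentures: "The special treatment will begin six months after completed radiotherapy, or later depending on the severity of the side effects".
- **Tests.** Under Study one, Data analysis: "For analysing changes over time the paired t-test or the Wilcoxon Signed Rank Test (for continuous variables", with McNemar for dichotomised variables. The same paragraph lists the t-test and Mann-Whitney test for two groups, and regression for prediction and confounding. It does not say which two forms are paired, or that the two-group tests use change or an earlier score.
- **Groups.** Participants gives 30 intervention patients and 30 matched controls, recruited at different centres. Design and setting declines a power calculation.

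**The concern.** The aim is the effect of prosthodontic rehabilitation. Between the baseline form and either follow-up form lie the extractions, radiotherapy, any surgery or chemotherapy, and side effects that the Introduction describes as possibly lifelong (dry mouth, altered taste, restricted opening). A change from baseline in one group adds all of these to any denture effect. A helpful denture could appear as no change or as a worsening, and relief from dental infection could appear as a benefit.

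The measurement closest to a pre-denture value is the form at about 6 months. It falls at the same nominal time as the earliest start of fixed treatment, and the visible text gives no order. A form answered after the first procedure would no longer be a clean starting value, and this could happen in the intervention group only. A later analysis plan can choose the pairing and the covariates, but it cannot recover a pre-procedure score that was never collected.

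**Working it through.** The protocol states no power, effect size or SD, so there is no figure of its own to reproduce. The check has three parts.

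**1. Order of events, taken from the text**

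| Time | Event |
|---|---|
| Before any treatment | Baseline form |
| Then | Extraction, then radiotherapy, with or without surgery or chemotherapy |
| About 6 months after radiotherapy | First follow-up form |
| 6 months after radiotherapy or later | Fixed treatment begins (intervention group only) |
| About 12 months, or in severe cases after one month of prosthesis use | Later form (the sentence does not say outright which form the exception concerns) |

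Baseline to 6 or 12 months spans the cancer course. Only 6 to 12 months leaves out extraction and radiotherapy, and only if the 6-month form precedes the first fixed-denture procedure.

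**2. What a one-arm paired test does when dentures have no effect**

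Inputs: n = 30 (Participants); level 0.05 (Data analysis), taken as two-sided; a common shift m from cancer treatment or recovery, in SDs of the change score (assumption). The rejection rate comes from the noncentral t distribution with 29 degrees of freedom and noncentrality m√30. For comparison, a two-sample t-test on the changes, 30 against 30 with the same shift in both groups, was simulated 20,000 times per value of m.

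| m (assumed) | One-arm paired test rejects | Between-group test of changes rejects |
|---|---|---|
| 0.2 | 18.5% | 4.8% |
| 0.3 | 35.5% | 5.2% |
| 0.5 | 75.4% | 4.9% |
| 0.8 | 98.8% | 5.0% |

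The paired test detects the shift whatever its cause. The between-group test keeps its level if the shift is equal in both groups, which is itself an assumption because the groups are not randomised.

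**3. What adjustment for the 6-month score gains**

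95% half-width of the group difference, in SDs of the 12-month score: 1.96 × √(2/30 × (1 − r²)), where r is the correlation between the earlier score and the 12-month score (assumption).

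| Analysis | r | 1 − r² | Half-width |
|---|---|---|---|
| Unadjusted | – | 1 | 0.51 |
| Adjusted for pre-treatment score | 0.3 | 0.91 | 0.48 |
| Adjusted for pre-treatment score | 0.4 | 0.84 | 0.46 |
| Adjusted for 6-month score | 0.6 | 0.64 | 0.40 |
| Adjusted for 6-month score | 0.7 | 0.51 | 0.36 |

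The formula takes all 30 per group as analysed, uses the normal quantile and ignores the matching. Its use is to compare the rows.

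**The case against.** The strongest reply is that the protocol never says the paired tests estimate the denture effect. It names no interval, and 6 to 12 months fits the wording as well as baseline to 12. A reader might infer that the denture conclusion is to rest on within-group change from baseline; the text does not support that. The design's means of separating dentures from the cancer course is the matched control group. Controls meet the same inclusion criteria, so they too have planned extractions and radiotherapy, and two-group tests and regression are listed. This stands. It confines the criticism of the paired tests to one possible reading.

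A reader might also infer that the 6-month form will be spoiled by implant surgery. The text does not support this either. Fixed treatment starts at six months or later, so most forms would come first. Some dentures are tooth-supported, so not every intervention patient has implant surgery. Appendix 13 may already set the order. One could calculate that a score 0.3 SD worse in one third of intervention patients adds 0.3 × 1/3 = 0.1 SD to the apparent 6-to-12-month gain. Both inputs are single guesses with nothing in the protocol behind them, and a plain 12-month group comparison would be unaffected. No weight is placed on that figure.

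Finally, the choice of pairs and covariates is often left to the analysis plan, and a pre-treatment baseline is not an error. Both points are fair. What remains for the protocol is the order of form and procedure, which is a matter of data collection.

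**Conclusion.** The point holds in limited form. If paired changes are taken from baseline, they describe the disease and treatment course and cannot by themselves show a denture effect. The control comparison can, but as written it is not tied to a post-radiotherapy, pre-denture score, and the visible text does not secure that score.

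The benefit of doing so is twofold. Adjustment reduces, without removing, bias from groups that are not randomised and come from different centres. It also narrows the half-width from about 0.51 SD to 0.36–0.40 SD, provided that r is 0.6 to 0.7. The rejection rates of 18% to 99% apply only to the one-arm reading and to the assumed shifts. The ordering gap is subject to appendix 13. This is an inexpensive improvement and does not show that the design fails.

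**What to change.** 1. In Study one, Data collection, state, consistently with appendix 13, that the form is completed at about 6 months after radiotherapy in both groups and, in intervention patients, before the first fixed-denture procedure. The treatment schedule is not changed. The form is not delayed when fixed treatment starts late, because that would make its timing differ between groups. Record the dates of form and procedure.
2. In Data analysis, base the denture conclusion on the between-group comparison of the later score adjusted for the 6-month score, by linear regression (ANCOVA), with the pre-treatment score as a further covariate.
3. Report within-group paired changes from baseline as descriptive only.

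The cost is a sentence or two of protocol text, a site instruction on the order of form and procedure, two recorded dates and slightly more analysis work. No new form is needed.

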Convergent validity: Spearman rank order correlations (ρ), assess convergent validity between (i) OHIP summary scores and self-reported health and (ii) OHIP subscale scores and subscale scores of the SF-36 and EQ-5D.

Study four – Cost-effectiveness analysis

Background

In order for a method in health- and dental care to be considered cost-effective, it has to be a decent relation between its extra costs and effects (no exact threshold value exist in Sweden). A cost-effectiveness analysis estimates the incremental cost-effectiveness ratio (ICER) of a method in comparison with the best option (33). The outcome measure can be of any (relevant) kind, but usually it is recommended to use quality-adjusted life-years (QALYs) which also is preferred by the Swedish Dental and Pharmaceutical Benefits Agency (34). QALY combines preferences for health states (QALY-weight) with the number of years of that health state.

In order to capture the full consequences of a treatment, it is often necessary to model future costs and effects into a longer time horizon. Even though these models cannot be seen as evidence, they can provide the most accurate estimate on the long-term cost-

effectiveness and they can furthermore handle uncertainty in order to provide a decision-maker with relevant information (35).

Data collection

Costs and effects of different prosthodontic rehabilitations, fixed and removable dentures, will be compared with costs and effects of radiotherapy of patients with head and neck cancer. Data on resource use will be gathered in the intervention and translated into costs, representing their best alternative use. Productivity loss of patients unable to work will be estimated using the human capital approach. The main outcome measure in the analysis will be QALY. QALY-weights are derived indirectly from the instruments EQ-5D and SF-6D, and directly from the EQ-VAS, all of which are analysed in Study one in this project. Other outcome measures that are more directly derived from oral health related quality of life will be used too in order to examine their relevance.

Data analysis

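### Study one tests every score at p<0.05 without naming a lead score or visit, and the shown text does not ensure that both groups have their later measurement at the same time

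*Protocol*

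**What the plan says.** The protocol's aim is "to evaluate the effect and cost effectiveness of prosthodontic rehabilitation on oral health related quality of life, general wellbeing, and nutrition". These outcomes are not ranked.

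Study one (Instruments) lists SF-36v2, EQ-5D, OHIP-14, GOHAI, JFLS-8 and OAS. SF-36v2 alone has eight domains and two summary indices. Study one, Data analysis, names two methods for the two-group case: "for comparison between two groups the Student t-test and the Mann-Whitney U-test". It gives no rule for choosing between them and closes with "The pre-chosen level of significance will be $p<0.05$ in all analyses".

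The only outcome called main anywhere is in Study four, the cost-effectiveness analysis: "The main outcome measure in the analysis will be QALY".

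On timing, Study one, Data collection, refers to appendix 13 (not among the pages shown) and summarises it as "measurements at approximately 6 and 12 months respectively, or in severe cases after the prostheses have been used for one month". The Fixed dentures section says "The special treatment will begin six months after completed radiotherapy, or later depending on the severity of the side effects" and "the fixture installation will be within a year after finished radiotherapy". The same section plans for removable dentures to be replaced by fixed ones inside the first year after radiotherapy. On controls, the Participants section says "If possible but not necessary, those controls may be prosthodontically rehabilitated with temporary removable dentures".

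**The concern.** The protocol sets an unadjusted per-test threshold for everything in Study one and does not say which result answers the question. With many related scores, two follow-up visits and two candidate tests, nothing in the text stops a single significant score from being presented as evidence that fixed dentures help.

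The choice of visit matters as well. A group difference at about 6 months has the same formal standing as one at about 12 months, yet fixed treatment has at most just begun by then. At the later visit, the allowance for severe cases ties the measurement to prosthesis use. A control without a prosthesis has no such reference point. If late intervention patients are measured later than controls, time since radiotherapy becomes mixed with treatment.

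**Working it through.** **1. Inputs.** From the protocol: level 0.05 for each analysis; 30 intervention patients and 30 matched controls (Participants); six instruments; follow-up at about 6 and 12 months. The protocol gives no family-wise error rate, power, effect size or SD, so there is no figure of its own to reproduce. Tests are taken as two-sided, which the protocol does not state.

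**2. Number of scores (a count, not a protocol figure).** One score per instrument gives 6. Using the SF-36v2 scores separately gives 8 domains + 2 indices + EQ-5D index + EQ VAS + OHIP-14 + GOHAI + JFLS-8 + OAS = 16.

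**3. Chance of at least one p<0.05 with equal group means.** For k independent tests it is 1 − 0.95^k. For k test statistics sharing one correlation ρ, with c = 1.96,

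P = 1 − ∫ [Φ((c − √ρ·z)/√(1−ρ)) − Φ((−c − √ρ·z)/√(1−ρ))]^k φ(z) dz.

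Results for the 12-month visit only:

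| Scores | ρ = 0.7 | ρ = 0.5 | ρ = 0.3 | ρ = 0 |
|---|---|---|---|---|
| 6 | 16.4% | 20.7% | 24.1% | 1 − 0.95^6 = 26.5% |
| 16 | 26.4% | 37.4% | 47.6% | 1 − 0.95^16 = 56.0% |

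A simulation of t-tests with 30 v 30 gave 16% and 21% for six scores, and 28% and 39% for sixteen, at ρ = 0.7 and 0.5. That agrees closely. The zero-correlation column is only a ceiling: the SF-36v2 indices summarise the same questionnaire as its domains, so these scores cannot be independent. The working range is ρ = 0.5 to 0.7, which is itself an assumption.

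**4. Two tests for one comparison.** Counting a comparison as significant when either the t-test or the Mann-Whitney test is below 0.05 raised the error of one comparison from 5% to about 6% (simulated normal data). This adds little to step 3.

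**5. Timing, side by side.**
- Fixed treatment starts at six months or later, and the first follow-up is at about six months. That visit is therefore at or before the start, and no fixed denture is yet in use.
- Replacement is planned inside the year, and the second follow-up is at about 12 months. An intervention patient who starts late may have had little use of the denture by then, or may be moved to the one-month-of-use rule.
- Controls need not have a prosthesis, so a rule based on prosthesis use cannot apply to all of them. If they stay on the ordinary 12-month rule, the two groups can be measured at different times since radiotherapy.

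**6. What one named comparison can detect.** By the normal approximation the standardised difference at 80% power is (1.960 + 0.842) × √(2/30) = 2.802 × 0.258 = 0.72 SD. With the noncentral t distribution it is 0.74 SD, and power for a 0.5 SD difference is 48%. Both figures are for an unpaired comparison without baseline adjustment, matching, site effects or loss to follow-up.

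**The case against.** **The error rates presuppose a success rule that the protocol does not contain.** This is correct. The protocol fixes a threshold per test and never says that any one hit means benefit. The figures are therefore conditional on that reading. What stands is that the text names nothing that would exclude it.

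**Higher rates, such as 56% or more, might be inferred.** The documents do not support them, because they need independent scores.

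**The 6-month visit might be called a design error.** It is not. The plan includes paired analyses of change over time, and a measurement after radiotherapy but before fixed treatment is a sensible reference for that. The narrower point stands: a group difference at that visit is not evidence about wearing fixed dentures.

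**The 12-month visit might be said to be defined differently for the two groups.** The shown text does not establish this. Appendix 13 may settle it, the plan is for replacement within the year, and the prosthesis-use rule is an exception for severe cases. A control without a prosthesis can follow the ordinary 12-month rule. What remains is a possible mismatch for late intervention patients.

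**This could be left to a statistical analysis plan.** A multiplicity method could be. But the protocol itself sets one threshold for all analyses and names no lead comparison, so the remedy changes a stated rule.

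**A power calculation was declined for a stated reason,** namely a restricted consecutive sample and time schedule. That is fair for choosing the sample size. A statement of the detectable difference would help readers but is optional.

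**Conclusion.** The point holds in this form. Study one has no lead score, visit or test, and applies p<0.05 throughout. If any single significant score at the 12-month visit were taken as benefit, the chance of at least one with equal group means would be roughly three to four times the nominal 5% for six scores (16–21%) and five to seven times for sixteen (26–37%). This rests on the score count, two-sided tests and assumed correlations of 0.7 to 0.5. Groups are formed by department, not by randomisation, so the true rate may differ.

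The timing part is conditional. The 6-month visit cannot show the effect of wearing a fixed denture. The later measurement may fall at different times in the two groups for late cases, unless appendix 13 prevents it. This is a worthwhile improvement to the protocol, not a flaw that invalidates the study.

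**What to change.** - Name one oral health related quality of life score, chosen by the investigators (for example the OHIP-14 summary score), at the approximately 12-month visit as the single primary between-group comparison in Study one. Test it once at two-sided 0.05 by one stated method.
- Report all other scores and visits as secondary estimates with 95% confidence intervals, without claiming an effect from single p-values.
- Reconcile the Fixed dentures, Participants and Study one Data collection sections, and appendix 13, so that the timing rule for the primary measurement applies equally to both groups, including controls without a prosthesis. The choice of timing is for the investigators.
- Optional: state that the sample is fixed by feasibility and that 30 per group give 80% power for about 0.74 SD in an unpaired, unadjusted comparison, and that this figure changes if baseline, matching or site is taken into account.

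The cost is protocol wording, with no extra patients or visits. The downside is that significance on the other scales can no longer carry the conclusion. The change limits multiplicity only and leaves confounding from allocation by department as it is.
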